Parkinson's disease is a neurodegenerative disease that results in various deficits, including cognitive impairments, for which there is a lack of interventions. Improvisational dance (ID) is spontaneously generated movement, similar to how one moves in everyday life. ID requires the integration of cognitive capacities to execute movements, and thus may strengthen cognitive processes involved in daily life function. ID has been shown to improve motor function in people with PD. The purpose of this study is to understand the effects of ID on cognition and daily function for people with PD. Specifically, it will test the effect of IMPROVment®, a method of ID designed for people with PD, on cognition and daily function. We will conduct a quasi-randomized wait-list controlled trial. Participants will be recruited and screened for eligibility through the St. Louis Chapter American Parkinson's Disease Association. Inclusion criteria includes: 50 years or older, PD diagnosis (mild to moderate), follows simple verbal cues, walks at least 3 meters independently, no contraindications in physical activity, mild cognitive impairment (determined by MOCA score), and no diagnosis of other severe comorbidities. The target sample size is 15-20 participants. Once enrolled, participants will undergo baseline testing (T1). Then participants will be randomly assigned to one of two groups: ID or waitlist control (WC). Participants in the ID group will begin a 12-week intervention where the group will meet once a week for a 1-hour IMPROVment® class. Participants in the WC group will continue with their regular routine for 12 weeks. After 12 weeks, all participants will complete Time 2 testing (T2; primary endpoint). Then WC participants will participate in the same IMPROVment® class for the following 12 weeks followed by Time 3 testing (T3; exploratory endpoint). For primary analysis, assessment scores will be compared across time point (T1, T2) and group (ID, WC) using mixed model ANOVA. Our results will provide further information on the effects of the IMPROVment® method for people with PD.

A2 Primary Hypothesis

The *central hypothesis* is that engagement in an improvisational dance (ID) class will benefit cognition and daily function among people with PD.

A3 Purpose of the Study Protocol

The purpose of this study protocol is to detail the various aspects of this study.

B Background

B1 Prior Literature and Studies

IMPROVment® was initially created for people with PD and has been used in several research studies since its conception^{4, 7, 14}. This method was developed by Christina Tsoules Soriano, a dance researcher, and is a standardized intervention used with a wide range of older adults. The proposed study will follow the protocol developed by its creators. IMPROVment® has been shown to have positive impacts on motor function in people with PD, but cognition and daily function have not yet been assessed. Because

IMPROVment® was developed specifically for people with PD and is centered around community engagement, physical and mental fitness, and freedom to create movement, it has high potential to improve the performance and participation of people with PD. Further, because it challenges cognition in ways that resemble the cognitive challenges of daily life, we hypothesize that it will be particularly beneficial for cognitive aspects of daily function. Furthering the evidence base for this method and demonstrating if it can be implemented by outside groups will increase its availability to the population of people with PD at large.

B2 Rationale for this Study

People with Parkinson's disease (PD) experience cognitive deficits.

Up to 50% of the 10 million people with PD experience cognitive deficits, specifically in visuospatial function, memory, and executive function^{1, 8-11}. Visuospatial function is the ability to identify and integrate the context of the surrounding visual space. People with PD experience increased difficulty in mobility due to decreased depth perception, inhibiting them from completing everyday activities safely and effectively⁸. Along with visuospatial deficits, people with PD experience memory issues, such as deficits in working memory, long-term memory, and procedural memory, which can inhibit them from completing familiar tasks, and learning new tasks⁸. The area in which cognitive deficits are often most prevalent in people with PD is executive function. Executive function consists of higher-order cognitive processes including, decision making, inhibition of unnecessary behaviors, and self-monitoring. Specifically, people with PD experience issues in multitasking, planning and organizing, and problem solving^{8, 11}.

PD-related cognitive deficits negatively impact daily function.

The progression of PD and associated level of impairment is highly individualized. People with PD experience impairments in areas of motor, affect, and cognition, all of which impact one's daily function. Daily function includes one's *performance* of daily activities as well as their general involvement in daily activities and life situations (termed *participation*). Since PD is categorized as a movement disorder, research and clinical care often emphasize its motor deficits. Recent literature, however, suggests that cognitive deficits, and specifically executive dysfunction, present the most problems in everyday life for people with PD^{2, 12}. Executive function largely contributes to how one carries out his/her daily functions. Dysfunction in this area of cognition can be detrimental to an individual with PD's engagement in everyday life. Research shows that executive dysfunction contributes to reduced social engagement, leisure participation, and issues with instrumental activities of daily living (iADL's), such as medication management and meal preparation^{2, 3, 12}. Due to its negative effects on daily function, effective interventions to address cognition in PD are imperative.

Dance is an emerging intervention for people with PD.

Dance is emerging as a potential therapy for people with PD. Dance is thought to be particularly effective because of "its entertaining nature and facilitation of participants' involvement"¹⁶. This notion is supported by evidence showing that participants have more consistent attendance and motivation for dance compared to more traditional exercise programs¹⁷. Evidence supports the use of several styles of dance as therapy, including, but not limited to, tango, ballet, and modern^{5, 6, 13, 16, 17}. The various styles of dance emphasize different types of movement tempos, dynamics, and postures, as well as cognitive processes. In this way, dance may address a wide range of daily functions

since activity performance and participation require a variety of movements and cognitive processes.

In line with the traditional focus on motor function in PD, much of the literature and evidence on dance as an intervention for PD emphasize physical deficits⁵. For example, dance has been associated with significant improvements in gait and balance for people with PD^{5, 13}. However, dance is not only a motor task but also requires the integration of cognitive processes to learn, plan, and execute movements. Cognition has been included as a secondary outcome in several studies of dance, and improvements in processing speeds in motor planning and judgement and cognitive task switching have been observed^{5, 13}. Researchers in the field have called for studies to focus explicitly on the cognitive effects of dance for people with PD because of the growing amount of evidence suggesting non-motor improvements with dance^{6, 14, 15}.

Improvisational Dance (ID) may be particularly effective for addressing cognition and daily function in people with PD.

People live their lives based on unplanned, natural movement. For people with PD, this lack of structure can present problems with everyday activities, such as functional mobility and iADL tasks. ID is spontaneous movement that is thought of and executed on the spot. Movement in ID challenges motor planning, decision making, and flexible thinking that “builds on the idea that daily living requires flexible, adaptive responses to real-life challenges”¹⁴. This direct application of ID to real life may render ID a particularly beneficial form of dance for people with PD. This idea is supported by Joan Toglia’s Dynamic Interactional Model, which looks at cognition in terms of the interaction between the person, activity, and the environment²⁰. In practice, this frame of reference is used to build cognitive strategies that apply to varying situations. In ID classes, participants may benefit from the strategies given in class and apply them to real-life situations. Further, the free movement of ID requires the participant to use higher order cognitive processes and by challenging these processes, we may strengthen them.

Another benefit to ID classes is that there is no right or wrong, and no set movements. These features allow free expression through movement and broad accessibility to the population of people with PD in which there is a wide range of functional capacity. Participants involved in more structured dance classes have reported feeling overwhelmed by the strict nature of the class, so they may prefer the self-determination of ID¹⁴.

Community-based programs promote activity engagement among people with PD.

Aside from dance itself, ID classes provide a fun, social form of activity engagement for participants. Research shows that people with PD that engage in PD-specific community-based programs are more likely to participate in everyday activities and roles^{21, 22}. Not only does participation in community-based programs increase activity participation, research suggests that community engagement increases participation in activities that people with PD ceased at the onset of their diagnosis²².

C Study Objectives

C1 Primary Aim

Investigate the effects of IMPROVment® on cognition for people with PD.

To test this aim, participants’ cognition will be assessed using the NIH Toolbox Cognitive Battery (NIH (CB)), the Alternate Uses Task (AUT), and the Weekly Calendar Planning

Activity (WCPA). Cognitive test scores will be compared across time points (T1, T2) and between groups (ID, WC) using a mixed model repeated measures ANOVA. We hypothesize that IMPROVment® will have positive effects on the cognitive abilities of people with PD.

C2 Secondary Aim

Investigate the effects of IMPROVment® on daily functions for people with PD.

Participants will also complete two questionnaires to assess daily function: Older Americans Resources and Services Scale- Extended Version (OARS-Ex) and PROMIS Satisfaction with Participation in Discretionary Social Activities (SPDSA). These scores will be compared similar to the above aim. We hypothesize that IMPROVment® will have positive effects on daily function in people with PD.

C3 Rationale for the Selection of Outcome Measures

The following table details the outcome measures involved in this study. Members of the research team have been trained in the following measures.

Assessment	Description
NIH (CB)	A comprehensive, performance-based test comprised of motor, emotion, sensation, and cognition assessments. For the purpose of this study, we will be using the cognitive battery to assess processes involved in learning and comprehension (i.e. thinking, remembering, problem-solving, judging). The battery consists of tasks involving the use of executive function, memory, attention, and language.
AUT	A verbal test of divergent thinking where the participant is given the name of an object and must name as many uses of that object as possible in a 3-minute time period. This assessment measures verbal fluency, originality, flexibility, and elaboration.
WCPA	A performance-based measure that assesses an individual's level of executive function. The task involves entering a list of errands into a calendar while following rules, keeping track of time, and managing conflicts.
OARS-Ex	A self-report questionnaire-based assessment that assesses perceived performance in ADL and iADL tasks by reporting the level of difficulty that they experience while completing the specific activity. Areas assessed include ADL tasks (walking, eating, dressing, grooming, getting in and out of bed, bathing, and toileting) and IADL tasks (using a telephone, traveling, shopping, preparing meals, housework, managing medication, and handling money) ¹⁸ .
SPDSA	A self-report questionnaire that assesses satisfaction with leisure activities and relationships with friends.

D Investigational Agent

NA

E Study Design

E1 Overview or Design Summary

This is quasi-randomized wait-list controlled trial. Once enrolled, participants will undergo T1 assessments consisting of the primary outcome measures for each aim (described above and attached) and other relevant factors (e.g. demographics, clinical characteristics, motor function). Participants will be randomly assigned (coin flip) to one of two groups: ID or WC group. Although our aim is to randomize participants to the different groups, if someone has a strong preference or inability to participate in one group or the other due to scheduling issues, we will try to accommodate his/her preferences. Each group will have 7-10 participants, a typical size for ID classes. This ensures enough participants to create a cohesive group, but also to provide an appropriate level of safety. The ID group will participate in a 12-week intervention where the group will meet once a week for a 1-hour IMPROVment® class. Participants in the WC group will continue with their regular routine for 12 weeks. After 12 weeks, all participants will complete T2 testing. Then WC participants will participate in the same IMPROVment® method for the following 12 weeks followed by T3 testing.

E2 Subject Selection and Withdrawal

2.a Inclusion Criteria

Inclusion criteria for this study include over 50 years old, PD diagnosis with Hoehn and Yahr stage 1-3 (mild to moderate), independently walks at least 3 meters and ability to comprehend and follow simple verbal cues.

2.a Exclusion Criteria

Exclusion criteria of this study include, a Montreal Cognitive Assessment score less than or equal to 21 (indicating cognitive impairment that may interfere with class participation), diagnosis of other severe comorbidities, and contraindications to physical activity. In addition, participants must attend at least ten of the twelve classes for their data to be included in analysis (they will still be allowed to participate in the classes).

2.b Ethical Considerations

Participants will be given the choice to be involved in the study and may withdraw at any time without penalty.

2.c Subject Recruitment Plans and Consent Process

Participants will be recruited and screened for eligibility through the St. Louis Chapter American Parkinson's Disease Association (APDA). Approximately 15-20 participants diagnosed with PD will be recruited for this study. Consent will be obtained from each participant by select members of the research team. Each participant will be walked through the informed consent document in detail and allowed to ask questions with no cohesion. Participants will be re-assented to additional research processes after 9.24.2019 upon IRB reapproval.

2.d Randomization Method and Blinding

After consent is given and T1 testing is completed, participants will be randomly assigned (coin flip) to either participate immediately (i.e., starting the next week) in 12-weeks of IMPROVment (ID group) or to continue with regular routine for 12 weeks before starting IMPROVment (WC group). Once we reach 10 participants in a group, remaining participants will be assigned to the other group. In addition, if the participant would like to be a part of this study, but can only participate in one group or the other, we will try to accommodate his/her needs.

2.e Risks and Benefits

Risks:

Participation in this study could result in the following risks. In addition to these, there may be other unknown risks, or risks that we did not anticipate, associated with being in this study.

One risk of participating in this study is that confidential information about participants may be accidentally disclosed. We will use our best efforts to keep the information about participants secure.

Another risk of participating in this study is an increased risk for falls. Although we do not expect the participants to fall during the intervention, precautionary measures are in place to decrease this risk (i.e. certified therapist present at all times, OT students monitoring the participants, movement modifications sitting in a chair).

Benefits:

Participants will not directly benefit from being in this study. Participants may indirectly benefit from participating in this study with the increased social participation and entertaining nature of the study program.

However, we hope that, in the future, other people might benefit from this study because it will help to provide information on how people with PD can best learn and remember in their daily lives.

2.f When and How to Withdraw Subjects

Participants may withdraw from this study at any time. To withdraw, participants will tell a member of the study team that he/she is no longer interested in participating in the study. He/she may withdraw completely from the dance classes or continue to dance and just withdraw from testing.

2.g Data Collection and Follow-up for Withdrawn Subjects

Data already collected on participants who withdraw from the study will be securely stored in a RedCap database. With the participants' consent, they may be used for comparison to those who remain in the study or for description of those who withdraw. If a participant would like to withdraw their data, they will be equipped with the procedure to follow on the Human Research Protocol Office website.

E3 Study Drug

NA

F Study Procedures

F1 Screening for Eligibility

Participants will be screened for eligibility using the “Inclusion/Exclusion Criteria Referral Form: IMPROVment® Class Participation” (Appendix 1)

F2 Schedule of Measurements

T1 testing will include the collection of demographics information, National Institute of Health Toolbox Cognitive Battery, the Weekly Calendar Planning Activity, Alternate Uses Task, and the Unified Parkinson's Disease Rating Scale Section 3 Motor exam.

Participants will also be asked to complete the Older Americans Resources and Services scale, Satisfaction with Participation in Discretionary Social Activities scale, the Parkinson Anxiety Scale, the Sleep Disturbance Scale, the Parkinson's Disease Fatigue Scale and the Depression Scale questionnaires. These questionnaires can be completed prior to the first day of intervention via RedCap survey mode or on paper if preferred. In addition, participants will be asked to complete a brief mood questionnaire at the beginning and end of each class. The participant will mark how they are feeling on 4 scales (see Appendix 4).

After the first 12 week period of intervention, both groups will be invited back to complete those same assessments (T2). After the second 12 week period, only the WC group will T3 testing with the same assessments.

F3 Class Structure

Classes will take place at the APDA in their group fitness room. Participants will use chairs and music during the class. Class will be instructed by an occupational therapy (OT) student that has trained as a dancer for 20 years and is certified to administer the IMPROVment® method after attending an in-person training by its original creators and continues to receive feedback to better the administration of IMPROVment®⁷. Class will begin and end with participants sitting in a circle formation to eliminate any feelings of hierarchy among the participants by creating a unified group. The classes consist of three parts: seated exercise, standing barre work, and across the floor movement (refer to Table 1). Movement cues are given by the instructor to the participants and progress through the themes of isolation, shape, time, flow, space/direction, and effort (refer to Table 2). Classes will be structured by using a set class protocol created by the IMPROVment team to ensure consistency in the method delivery. Music that is popular with the age demographic will be played throughout the entire class. Trained OT students in the Cognitive and Occupational Performance Lab (PI: [name]) and the APDA's certified physical therapist ([name], DPT) will attend all classes to ensure participant safety.

Please see Appendix 2 for a detailed list of exercises that comprise class structure.

F4 Safety and Adverse Events

4.a Safety and Compliance Monitoring

Trained occupational therapy graduate students in the Cognitive and Occupational Performance Laboratory (PI: [name]) and the APDA's certified physical therapist ([name], DPT) will attend all classes to ensure participant safety. We do not anticipate any serious adverse events; however, class participation may increase the risk for falls and minor resulting injuries (e.g., bruises, scrapes). We expect this occurrence to be low if at all present, as the participants have relatively low fall risk and precautionary measures are in place to prevent falls (i.e. certified PT and OT students present at all times to monitoring participants' safety, safety modifications [e.g. sitting in a chair]).

4.b Medical Monitoring

NA

4.c Definitions of Adverse Events

NA

4.d Classification of Events

NA

4.e Data Collection Procedures for Adverse Events

See Adverse Event Reporting Form in Appendix 3. Data on the number and type of adverse events will be collected and reported when study results are disseminated.

4.f Reporting Procedures

See Adverse Event Reporting Form in Appendix 3.

4.g Adverse Event Reporting Period

Adverse events will be reported to the PI immediately (within one day), and the participant will be encouraged to report them to his/her primary care physician or neurologist within the week.

4.h Post-study Adverse Event

NA

G Statistical Plan

G1 Sample Size Determination and Power

Each group will have 7-10 participants, a typical size for ID classes. This ensures enough participants to create a cohesive group, but also to provide an appropriate level of safety. Since this is a pilot study, power analyses were not conducted. Rather, data from this study can be used to power future studies. Although attrition is not anticipated, we aim to recruit 10 participants per group to ensure there are at least 7 participants in the class.

G2 Interim Monitoring and Early Stopping

NA

G3 Analysis Plan

Aim 1: Investigate the effects of IMPROVment® on cognition for people with PD.
Cognition will be assessed at pre (T1) and post (T2) using the NIH (CB), AUT, and WCPA. Scores obtained in these assessments will be compared across time point and group using mixed model ANOVA.

Aim 2: Investigate the effects of IMPROVment® on daily functions for people with PD.
Daily function will be measured at pre (T1) and posttest (T2) using the OARS-EX and SPDSA. Scores will be compared across time point and group using mixed model ANOVA.

G4 Statistical Methods

See above. Analysis will be conducted with IBM SPSS software.

G5 Missing Outcome Data

Participants with missing data will be excluded from analyses involving those data. Since this is a small pilot study, we intend to maximise the use of data we can collect.

G6 Unblinding Procedures

NA (this is not a blinded study)

H Data Handling and Record Keeping

H1 Confidentiality and Security

Confidentiality will be maintained in accordance with applicable state and federal laws. Subject data will be coded numerically to protect individual identity. No identifiers will be used in presentation or publications. All data will be stored in locked cabinets or on computers within a private, secure network protected by a PIX firewall with remote access only permitted through virtual private network connections, as per HIPAA guidelines. Patients will be informed of all risks prior to participation. Subjects will be told that they may discontinue participation at any time, that they have the alternative not to participate in the study, and that this will not impact their medical care. All key personnel involved in the design or conduct of research involving the human subjects will receive

the required education on the protection of human research participants and HIPAA guidelines prior to funding of this project. Consent will be obtained in a private setting in the room where the experiment will take place. Data will be stored in REDCap on the secure WUSM server.

A photographer will attend class to capture images of the intervention. All participants have signed a photo release forms for the APDA and will sign a photo release form for Washington University (Appendix 5).

H2 Training

Members of the research team will be trained in the assessments and/or how to assist during the dance classes prior to the start of the study. Testers will watch training videos, practice administering the tests, and perform a checkout assessment that is reviewed by an expert.

H3 Case Report Forms and Source Documents

NA

H4 Records Retention

Data collected under this protocol will be kept for a minimum of 7 years after the study is complete.

H5 Performance Monitoring

NA

I Study Monitoring, Auditing, and Inspecting

NA

J Study Administration

J1 Organization and Participating Centers

This study will take place in the following locations: Washington University in St. Louis School and Medicine and the American Parkinson's Disease Association St. Louis Chapter.

J2 Funding Source and Conflicts of Interest

J3 *Lee Silverman Voice Treatment (LSVT) Global is funding this research study. This means that Washington University is receiving payments from LSVT to support the activities that are required to conduct the study. No one on the research team will receive a direct payment or increase in salary from LSVT for conducting this study. Committees*

NA

J4 Subject Stipends or Payments

Subjects will be given a check for participating in this study.

J5 Study Timetable

Recruitment will occur once the IRB is approved through approximately August 2019, and the study will begin in September 2019. This will ensure ample time for participants to consider participating in the study. Participation in this study is completely voluntary and that will be verbally told to each participant and on the written consent.

Prior to the start of the study, research team members will be trained and checked out on each assessment and the use of RedCap.

Baseline testing will occur in late August 2019, allowing the intervention to begin in September 2019 and run for the following 12 weeks until November 2019. Post testing will occur in that following week. Due to the holiday season and school schedules, the control participants will begin the second wave of intervention in January 2020 until March of 2020.

K Publication Plan

The research team plans to publish findings from this study at its completion.

L Attachments

L1 Tables

Table 1. IMPROVment® Class Components

Components	Class Description
Seated Exercise	Class begins with all participants seated in a chair. Movement cues are given to move different parts of the body in different qualities (i.e. sharp and soft). This part of class serves as a warm up for the body prior to engaging in bigger movements.
Standing Barre Work	Movement progresses from a seated position to standing while still holding onto the chair for extra support. Barre work begins to

	test balance abilities and increase level of movement executed (i.e. balancing on one leg).
Across the Floor	This is the section of class in which ID is incorporated most in several movement activities. These ID tasks are done both individually, in partners, and as a large group. Participants are not limited to staying close to their chairs and move around throughout the space using ID movement (i.e. moving in sync with another person in the room).

Table 2. IMPROVment® Class Themes

Class Themes

Class Themes	Description
Isolation	Movement of a specific body part or parts.
Shape	How the body moves as a whole, as a combination of body parts, or as individual body parts. Shape can also be impacted by other objects in the environment (i.e. chairs, walls, other participants).
Time	The relationship between the body's movement and music. Time can also be impacted by the movement of other participants.
Flow	The transition between movement, specifically the continuity of movement.
Space/direction	The connection of movement to the physical environment. This is how movement is carried through space in both a stationary, seated position and locomotion throughout the classroom.
Effort	The movement quality (i.e. light, heavy, free, structured).

L2 Appendices

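### Participants may be placed without the coin flip, but the route is not recorded and no randomised-only analysis is planned; separately, the capped flip does not secure 7-10 per group at 15 or 16 recruited

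*Combined protocol and SAP*

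**What the plan says.** E1 declares the design openly: "This is quasi-randomized wait-list controlled trial". Assignment is by coin flip, but E1 says the team will try to accommodate preferences "if someone has a strong preference or inability to participate in one group or the other due to scheduling issues". Section 2.d gives a narrower-sounding exception, for a person who "can only participate in one group or the other, we will try to accommodate his/her needs". Neither section limits how many people may be placed this way.

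Section 2.d also caps the groups: "Once we reach 10 participants in a group, remaining participants will be assigned to the other group". E1 and G1 state 7-10 participants per group, and section 2.c gives a total of about 15-20. G1 adds: "we aim to recruit 10 participants per group to ensure there are at least 7 participants in the class".

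For Aim 1, G3 says: "Scores obtained in these assessments will be compared across time point and group using mixed model ANOVA". Aim 2 is handled the same way. G3 and G4 contain no term, subset or sensitivity analysis by allocation route. The route is not among the items collected in F2, case report forms are marked not applicable in H3, and the referral form in Appendix 1 does not ask about availability.

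**The concern.** The T1-T2 comparison between groups is what the trial will report for both aims. Randomisation protects it only for those who were randomised. A stable baseline difference between accommodated and randomised participants cancels in the group-by-time term. A difference in expected change does not cancel unless it is balanced across the groups. Because the study is open, and OARS-Ex and SPDSA are self-reported, such a difference is possible and would look like a class effect. If the route is not written down at allocation, neither the sponsor nor a reader can examine this afterwards.

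The second matter is separate. The stated group range, which E1 and G1 tie to group cohesion and safety, does not follow from the allocation rule at every total inside the recruitment target.

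**Working it through.** **1. Group sizes under the stated rule**

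Inputs: a coin flip (assumed fair), a cap of 10 (2.d), a total N of 15-20 (2.c), a stated range of 7-10 per group (E1, G1), nobody accommodated and no attrition.

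The smallest possible group is N - 10: 5 at N=15, 6 at N=16, and 7 to 10 at N=17 to 20.

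- N=15: both groups reach 7 only with a 7/8 split. Probability 2 × C(15,7)/2^15 = 12,870/32,768 = 0.393. Chance that a group is below 7: 0.607.
- N=16: both reach 7 only with 7/9 or 8/8. Probability (2 × 11,440 + 12,870)/65,536 = 0.545. Chance that a group is below 7: about 0.45.
- N=17-20: 0, because the cap forces the smaller group to at least 7.

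The rule therefore gives 5-10 per group over the stated totals, and the stated 7-10 is not reproduced. With 2 to 4 people accommodated before the flips (an assumption), the chance is 55-76% at N=15 and 39-63% at N=16, depending on where they are placed.

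**2. Possible bias from accommodation**

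The documents give neither the share accommodated nor any difference in change, so both are assumed. The unit is the SD of the T1-T2 change.

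Bias = (share of ID accommodated × their extra change) - (share of WC accommodated × their extra change).

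With ID only, shares of 10-40% and extra change of 0.3-0.8 SD, this runs from 0.10 × 0.3 = 0.03 SD to 0.40 × 0.8 = 0.32 SD.

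With two time points, the group-by-time test is equivalent to a two-sample t test on change scores. Type I error at a nominal two-sided 5%, 10 per arm, from 400,000 simulated trials:

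| Accommodated | Extra change (SD) | Bias (SD) | Type I error |
|---|---|---|---|
| None | - | 0 | 5.0% |
| 1 in ID | 0.5 | 0.05 | 5.0% |
| 2 in ID | 0.5 | 0.10 | 5.2% |
| 3 in ID | 0.5 | 0.15 | 5.8% |
| 4 in ID | 0.5 | 0.20 | 6.7% |
| 4 in ID | 0.8 | 0.32 | 9.1% |
| 2 per arm, opposite directions | 0.5 | 0.20 | 6.5% |
| 3 per arm, opposite directions | 0.5 | 0.30 | 8.8% |
| 2 per arm, same direction | 0.5 | 0 | 4.6% |

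**3. What a randomised-only analysis can show**

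95% CI half-width = t(0.975, n1+n2-2) × sqrt(1/n1 + 1/n2), in SD of change.

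- 4 of 20 accommodated: 0.94 (10/10) becomes 1.07 (8/8, two from each group) or 1.11 (6/10, all from ID).
- 4 of 15 accommodated: 1.12 (7/8) becomes 1.37 (5/6), 1.42 (4/7, all from the group of 8) or 1.53 (3/8, all from the group of 7).

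Dropping the accommodated lowers mean squared error only if the bias exceeds sqrt[(1/m1 + 1/m2) - (1/n1 + 1/n2)], where m1 and m2 are the group sizes left:

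- 10/10 to 8/8: sqrt(0.250 - 0.200) = 0.22 SD
- 10/10 to 6/10: sqrt(0.267 - 0.200) = 0.26 SD
- 7/8 to 5/6: sqrt(0.367 - 0.268) = 0.31 SD
- 8/7 to 4/7: sqrt(1/4 - 1/8) = 0.35 SD
- 7/8 to 3/8: sqrt(1/3 - 1/7) = 0.44 SD

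Four in ID at 0.5 SD gives a bias of 0.20 against a break-even of 0.26. Two per arm in opposite directions gives 0.20 against 0.22. In both, keeping everyone gives the lower mean squared error.

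**The case against.** The departure is declared, the study is a pilot with no power analysis, and accommodating people who can attend only one class series is a reasonable feasibility choice. G5 says "we intend to maximise the use of data we can collect". The bias is small under most assumptions, and the randomised-only estimate will usually be too imprecise to show whether accommodation mattered. All of this stands. It lowers the weight of the point and argues against making the randomised-only analysis the main one. It does not answer the recording gap: the design label tells a reader that some people may not have been randomised, but not who or how many. G1 also intends the data to inform the power of later studies, and section K plans publication.

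On group size, G1 aims for 10 per group, where the problem disappears. That too stands, but 15 and 16 are within the stated target.

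Four stronger readings are tempting, and the documents do not support them:

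- A reader might infer that people placed in WC have competing commitments that affect their measured change, since J5 puts T1-T2 in September-November. The class is one hour a week, and nothing links a clash with that hour to cognition or daily function.
- A reader might infer that E1 and 2.d contradict each other on preference. In E1 the scheduling clause can qualify both preference and inability, in which case the sections agree. Clarification is all that is needed.
- A reader might infer that the cap lets staff steer late enrolments. Section 2.d puts consent and T1 testing before assignment, and no consequence can be shown.
- A reader might infer that F2's questionnaire deadline conflicts with assignment after T1. It is an outer limit and is compatible with that order.

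**Conclusion.** The point holds as a gap in recording, reporting and sensitivity analysis, at the lower end of what should be fixed. The plan permits an unlimited number of placements without the flip, compares everyone by group, and leaves no means of checking the effect. That G3 pools the two routes is inferred from its silence, but the text offers no other reading. The size and direction of any bias are unknown. With 10 per arm and the assumed shares and drifts, type I error is about 5-7% in most scenarios and about 9% at the extremes, and balanced accommodation cancels. The documents do not support calling the comparison invalid or biased in a known direction.

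Separately, the capped coin flip misses the stated 7-10 per group with probability 61% at N=15 and 45% at N=16, and never at 17-20. This assumes a fair coin, no attrition and nobody accommodated.

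**What to change.** 1. Before allocation, ask each volunteer whether they can attend both class periods in J5. State in E1 and 2.d, in the same words, whether preference alone qualifies for accommodation.
2. After T1, allocate everyone who can accept either group by one concealed draw to group totals fixed in advance inside 7-10 and as near equal as possible. With nobody accommodated this gives 7/8 at N=15, 8/8 at N=16 and 10/10 at N=20.
3. Record the allocation route (drawn or accommodated) for each participant and report it by group.
4. Add to G3 a pre-specified randomised-only T1-T2 analysis as a supportive sensitivity analysis. Keep the all-participants analysis, and describe it as not fully randomised if anyone was accommodated.

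The cost is protocol wording, one screening question, one randomisation list, one data field and one extra analysis. J5 already places baseline testing in late August before a common September start, so a single draw fits the timetable. The drawback is precision: given the half-widths above, the added analysis can show consistency but will rarely be decisive. Items 1 and 3 carry most of the value.

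These changes do not touch the separate selection after allocation from the rule that "participants must attend at least ten of the twelve classes for their data to be included in analysis". If that rule removed two more from ID, an 8/8 comparison would become 6/8, with a half-width of 1.18 SD.
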